Aim 1a. and 1b. The outcome measures involved in this aim (e.g., parenting self-efficacy measured using the PMP S-E and perceived stress scale), are derived from multi-item scales and will be treated as continuous measurements. For each scale, the mean score after baseline will be assessed at each of the visits (1 week, 1 month, 3 months, 6 months and 12 months). The overall mean difference from baseline for each of the scales between the two intervention groups will be used to evaluate Aim 1. We will assess the overall change in scores for the self-efficacy and depression scales, i.e. the population averaged effect of the intervention on changes in self-efficacy and depression, using a generalized estimating equation (GEE) model to account for the correlation between the repeated change measurements among primary care givers. The GEE model is reasonably robust to missing data. We will use an exchangeable correlation structure, but in sensitivity analyses, will also test unstructured correlation and compare parameter estimates. The main independent variable in these analyses is intervention group, however we will also include (if necessary) a cross-product term of group-by-time which will enable us to estimate differences between the intervention groups over time. The group-by-time term will be included only if it is statistically significant. The model will include covariates reflecting the randomization stratification variables, and other covariates only if imbalances are observed in the randomization groups at baseline. In addition, we will use the model to plot the change in parental self-efficacy or parenting stress over time-by-group with 95% CI around each time point estimate. The degree of change at 3-months will allow us to assess the rapidity of any effect of intervention and a descriptive comparison of the differences between the groups at 6- and 12-months will allow us to assess the degree of persistence of any effect. We will consider the difference between groups to be statistically significant when the 95% confidence intervals around the difference do not include 0.

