Aim 2a. and 2.b. will compare measures of anxiety using the STAI, and depression using the CES-D in primary caregivers from the intervention and control groups. The independent variable will be the intervention group in both models. If necessary, the models will include covariates known to impact parental depression and anxiety (if different between the groups) and stratification variables. We will estimate and compare the covariate adjusted mean difference in the scores between the intervention

groups using GEE models as described above (Aim 1). The difference will be considered to be statistically significant if the 95% CI around the difference fails to include 0.

As in Aim 1, group-by time-interaction models will be used to evaluate differences between the groups over time.

Aim 3. The NICU graduates may experience multiple ED visits or hospitalizations any time after baseline. The number of ED or hospitalization counts will be summed for each of the intervention groups. To assess differences between the intervention groups for each of the outcomes (ED visits or hospitalizations), we will use the Wilcoxon–Mann–Whitney two-sample rank-sum test, which is appropriate for use with nonparametric data, such as the count data from this aim. We will define the outcome, improved immunization status, as receipt of two diphtheria-tetanus-acellular pertussis (DTaP) vaccines, two Hemophilus influenzae b (HIB) vaccines, and two pneumococcal conjugate vaccines (PCV-13) by the end of the observation period (12 months after baseline). This binary outcome will be contrasted using an unpaired t-test with unequal variances to measure the hypothesis that the intervention results in improved immunization status.

Sensitivity Analyses. In sensitivity analyses, we will explore the effect of departures from assumptions made for the main analysis. A key assumption in our analyses is that missing data are missing at random, and groups who are and are not lost to follow-up are similar. We will compare characteristics of families who are, and are not, lost to follow-up. If significant differences between these two ( $p < 0.05$ ) are observed, we can test for intervention effects, but with the assumption that individuals with missing data have worse outcomes. We will then report these ‘worst case’ scenarios and report any changes in the clinical interpretation of the trial.

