Sample Size & Power. We calculated power to detect projected differences between the intervention groups for the 3 primary outcomes. All computations are based on a projected sample size of 300 families of NICU infants (i.e. 300 primary care giver evaluations, and 300 NICU infant outcome evaluations) with randomization into 2 equal groups of 150, with data collected over multiple time points during the 12 months of follow-up post discharge. In Aims 1 and 2, we will have up to 5 repeated measures after baseline (1-week, 1-month, 3-months, 6-months, and 12-months), which increases our statistical power for those aims. We assumed a modest within-subject correlation of 0.50 between these repeated measures. Using Bonferroni correction, we adjusted alpha (0.05) for the number of primary outcomes,  $n=3$ . For Aim 1, we estimate that we will have excellent power (93%) to detect differences in parental self-efficacy scores as small as 0.33SD. This estimate is based on PMSPE score distributions as reported in the literature. For the main infant outcome of number of hospitalizations during the 12-month follow-up post discharge period, we estimate that we have excellent power (99%) to detect a difference of 1 in the median number of hospitalizations between the groups. Given our conservative assumptions, including modest correlation ( $r=0.5$ ) between repeated measures and Bonferroni correction for the number of primary outcomes, we believe that our sample size ensures sufficient power to measure clinically relevant differences between the intervention groups.

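### The Bonferroni alpha used for power is missing from the significance rules; the third primary outcome is unnamed, and the two power figures lack a stated basis

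*SAP*

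**What the plan says.** The Sample Size & Power paragraph of the SAP (Statistical Considerations), which the protocol repeats, opens: "We calculated power to detect projected differences between the intervention groups for the 3 primary outcomes". It goes on: "Using Bonferroni correction, we adjusted alpha (0.05) for the number of primary outcomes", that number being three, and later counts the correction among its conservative assumptions. The inputs are 150 families per group, up to five post-baseline measures and a within-subject correlation of 0.50.

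Two results follow: "we estimate that we will have excellent power (93%) to detect differences in parental self-efficacy scores as small as 0.33SD", and for the infants "we estimate that we have excellent power (99%) to detect a difference of 1 in the median number of hospitalizations between the groups". No power is given for a third primary outcome, and none is named. Self-efficacy and hospitalizations can be recognised as primary only because they appear here. The paragraph does not say whether the tests are one-sided or two-sided.

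On numbers: "All computations are based on a projected sample size of 300 families of NICU infants". The protocol's End Points section gives the same 300 as the enrolment target.

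The decision rules come earlier in the same SAP section:

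- Aim 1: "We will consider the difference between groups to be statistically significant when the 95% confidence intervals around the difference do not include 0".
- Aim 2: "The difference will be considered to be statistically significant if the 95% CI around the difference fails to include 0".
- Aim 3, for ED visits and hospitalizations: "we will use the Wilcoxon–Mann–Whitney two-sample rank-sum test", with no significance level.

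**The concern.** The plan uses one alpha to justify its size and another to declare success. The power paragraph presents the primary outcomes as multiplicity-controlled, but the paragraphs that decide significance contain no such control. Anyone following the decision rules tests the scale outcomes at two-sided 0.05, while anyone relying on the power paragraph would expect 0.0167. For a result between the two levels, the plan supports both a positive and a negative conclusion.

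Because the third primary outcome is unnamed, the family of tests that the correction covers is not fixed. The protocol's Specific Aims list eight hypotheses (1a to 3d), so the choice could be made after results are known.

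The two power figures are the only numerical support for 300 families. If their basis is not stated, a reader cannot tell what the trial can detect under the rule it will actually apply.

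**Working it through.** **1. Reproducing the 93%.** Inputs from the Sample Size & Power paragraph: n = 150 per group, m = 5, r = 0.5, effect 0.33 SD, alpha 0.05/3 = 0.0167.

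- Variance of the mean of five exchangeable measures: (1 + 4 × 0.5)/5 = 0.6 SD². For mean change from baseline, which the Aim 1 paragraph models, assume that the baseline also correlates at 0.5. The variance is then 0.6 + 1 − 2 × 0.5 = 0.6, the same.
- Standard error of the group difference: √(2 × 0.6/150) = 0.0894 SD.
- Standardised effect: 0.33/0.0894 = 3.690. Power = Φ(3.690 − z), from unrounded values:

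| Basis | z | 3.690 − z | Power |
|---|---|---|---|
| Two-sided 0.0167 | 2.394 | 1.296 | 90.2% |
| Two-sided 0.025 (Bonferroni for two, not three) | 2.241 | 1.448 | 92.6% |
| One-sided 0.0167 | 2.128 | 1.562 | 94.1% |
| Two-sided 0.05 (the written 95% rule) | 1.960 | 1.730 | 95.8% |

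A t distribution on 298 df changes these by 0.3 points or less. At two-sided 0.0167, 93% would need 166 analysed per group, or an effect of 0.346 SD.

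**2. Where the paragraphs disagree.** The chance that a scale result has p between 0.0167 and 0.05 is power at 0.05 minus power at 0.0167, both two-sided:

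- no effect: 5.0% − 1.7% = 3.3%
- true 0.20 SD: 60.9% − 43.7% = 17.2%
- true 0.33 SD: 95.8% − 90.2% = 5.6%

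**3. Familywise error.** Three tests at 0.05, independent: 1 − 0.95³ = 14.3%. With assumed correlations between the test statistics of 0.5 and 0.7, simulation gives 12.5% and 11.0%. At 0.0167 each, it is 1 − (1 − 0.0167)³ = 4.9% if independent. These figures assume that the hospitalization test would also be run at 0.05, since no level is stated.

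**4. Loss.** No rate is given, so the rates here are assumed. Power is at two-sided 0.0167. In the first column lost families give no post-baseline visit (135, 120 and 105 per group remain). In the second, dropout is spread evenly over 0 to 4 completed visits, and a family with k visits contributes information k/(1 + (k − 1) × 0.5).

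| Loss | No visits | Spread dropout |
|---|---|---|
| 10% | 86.6% | 89.1% |
| 20% | 81.8% | 87.8% |
| 30% | 75.6% | 86.4% |

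The 20% row in full. No visits: SE = √(2 × 0.6/120) = 0.100, and 3.30 − 2.394 = 0.906, giving 81.8%. Spread: mean information is 0.8 × 1.667 + 0.2 × 1.087 = 1.551, SE = √(2/(150 × 1.551)) = 0.0927, and 3.559 − 2.394 = 1.165, giving 87.8%.

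**5. Hospitalizations.** The documents give no admission rate or distribution. Simulated rank-sum power at 150 per group and two-sided 0.0167, every case having medians 1 and 0 (means assumed):

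- Poisson, 0.8 v 0.6: about 34%
- Poisson, 1.0 v 0.5: about 99%
- negative binomial, dispersion 1, 1.2 v 0.6: about 88%

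The same difference in medians fits very different powers, so it does not determine the figure.

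**The case against.** The strongest objection concerns the 93%. A reader might infer from the 90.2% that the plan overstates its power under its own two-sided rule. The documents do not support that. The only two-sided rule written down is the unadjusted 95% interval, and under it power is 95.8%, above 93%. The 90.2% combines the alpha of the power paragraph with the sidedness of the Aim 1 rule, a combination the plan never writes. Hypothesis 1a is directional, and a one-sided 0.0167 calculation gives 94.1%, close to the stated figure. The gap is also small against rounding of the inputs: at two-sided 0.0167, an effect of one third of an SD gives 90.9%, and r = 0.45 gives 92.3%. This objection stands. No arithmetic error is shown, only a missing basis.

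A reader might also infer that 300 families are too few. That is not supported either. Under the written 95% rule, power at 20% complete loss is still 91.0%. At two-sided 0.0167 it falls below 80% in the table above only if 30% of families give no post-baseline data. The SAP does address missing data through GEE and sensitivity analyses, though neither is an allowance for loss in the sample size.

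Nor is the 99% shown to be false. The 0.8 v 0.6 example was chosen so that the medians only just differ. If a difference of 1 means a shift of one admission, the usual rank-sum alternative, simulation under assumed means and dispersion gives 99.5-100%. The figure is plausible but undocumented.

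Finally, Bonferroni might have been meant only as a planning margin. The plan does not say so, and on that reading the primary outcomes have no multiplicity control at all. The alpha mismatch therefore survives.

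**Conclusion.** The point holds as an inconsistency between the power paragraph and the decision rules. The power paragraph claims a correction for three primary outcomes; the Aim 1 and 2 rules do not apply it, and the Aim 3 test has no level. The cost is in type I error and in clarity of conclusions, not in power. Familywise error is 14.3% rather than 5% if three independent outcomes are each tested at 0.05, and about 11-12.5% at the assumed correlations. The chance of contradictory verdicts on a primary scale peaks, among the effects examined, at 17.2% for a true 0.20 SD.

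Three further gaps are real but secondary. The third primary outcome is neither named nor given a power figure. The 93% is not reproduced at two-sided 0.0167, and its sidedness is not stated. All 300 enrolled families are counted as evaluated. The 99% can be neither confirmed nor refuted from the documents.

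The self-efficacy results rest on the plan's own inputs and a normal approximation. The loss rates, outcome correlations and admission distributions are assumptions made here.

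**What to change.** Amend the SAP, and the matching protocol text, as follows:

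- Name the three primary outcomes, give power for each, and label all other outcomes secondary.
- Apply one two-sided alpha of 0.0167 to both power and decisions: 98.3% confidence intervals for the primary scale outcomes, and p < 0.0167 for the hospitalization rank-sum test.
- Restate self-efficacy power on that basis: about 90% for 0.33 SD with 150 per group analysed, and about 82-88% at an assumed 20% loss, depending on when families are lost.
- State the control-group distribution assumed for hospitalizations and its source, and recompute that power at 0.0167. The simulated values above illustrate sensitivity only and should not become plan text.

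The cost is a few lines of text and no extra families. Primary scale intervals become 2.394/1.960 = 1.22 times as wide; for self-efficacy with no loss the half-width goes from 1.960 × 0.0894 = 0.175 SD to 2.394 × 0.0894 = 0.214 SD. The stated power becomes slightly less favourable.

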The evaluation of the Parent Navigation NICU to home program will use a randomized trial design. We will do so by recruiting a population of parents who have an infant in the Children's National NICU, half of whom will receive enhanced usual care by provision of a NICU care notebook and half of whom will receive the same enhanced care- including care notebook- plus Parent Navigation (intervention). All will be patients in the NICU who are discharged from the CNMC NICU. Group assignment will be by randomization, stratified by birth weight (≤ 1500 grams or >1500 grams). The design incorporates extensive measurement of baseline attributes to assess the comparability of intervention and enhanced control groups at inception.

We aim to enroll $n=300$ parents of infants receiving care in the Children's National NICU who are discharged from the CNMC NICU. CNMC has a Level IV NICU which receives a large number of complex cases. To allow for generalization of study findings to other NICUs and other centers, we will enroll all patients discharged from the CNMC NICU.

Study personnel will identify eligible NICU patients by reviewing NICU census data or through the use of the PowerTrials Prescreening function. PowerTrials is a HIPAA-compliant application that is integrated into the Children's National Cerner electronic medical records system (PowerChart). Study inclusion and exclusion criteria will be used to create a Prescreening Rule. A screening engine in PowerChart will compare the criteria to patient data within the medical records system, and a list of potential study subjects will be generated.

Research study staff will approach parents anticipating discharge within 1-2 weeks to invite their participation and, as appropriate, obtain informed consent. If parents of eligible patients are not available, we may contact a parent by phone to set up a time to discuss the study in person. We will obtain in person signatures of consent as appropriate before enrolling potential participants in the study. Recruitment will continue in this fashion until the required sample is enrolled.

Inclusion criteria include:

NICU patients discharged from the CNMC NICU. One parent participant per NICU patient will be identified and enrolled as the participant.

Exclusion criteria include:

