Participants will be reimbursed for their participation in data collection. Compensation will be \$20 per each data collection time point and \$50 for in person developmental assessment by [name] (Co-I) in Developmental Clinic at age 12-15 months. Our previous experience with longitudinal research in this population suggests that this amount provides adequate incentive without being coercive.

Infant health outcomes:

Infant health outcomes will include health care utilization (ED visits, hospitalizations, specialty visits, primary care visits) and immunization status.

- Health care utilization:

At each interview, parents will provide information about ED visits, hospitalizations, specialty visits, and primary care visits during the period since the prior interview. All parents/participants will be provided with a calendar to keep track of these encounters for easy recall. We will measure the total number of ED visits, hospitalizations, specialty visits, and primary care visits during the 12 month follow-up period post NICU discharge.

- Immunization status is a frequent measure for use of preventive medical care services and is easily verifiable. We will use receipt of vaccines between NICU discharge and 12 months of age as the outcome measure. We will consider receipt of 3 diphtheria-tetanus acellular pertussis (DTaP) vaccines, 3 Hemophilus influenzae b (HIB) vaccines, and 3 pneumococcal conjugate vaccines (PCV-13) as fully immunized. We will ask the primary caregiver to complete a release of medical information (for immunization records only) upon enrollment. We will obtain immunization records by sending the release to the primary care pediatrician or, when applicable, from the DC or Maryland immunization registry, which is available to Children's National health care providers with a password.

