Parent Navigation: Once parents/patients are enrolled, all participants will receive a NICU care notebook as described above. Within 24 hours, using a REDCap-based randomization schema built by [name] (Co-I) and blinded to the rest of the study team, participants will be randomized to either the control or intervention group. Those randomized to the control group will not receive any Parent Navigation care but will receive the usual care offered in the NICU. Study personnel will notify control participants of their assignment to the control group. We do not want to add any additional stress for these families, and if left wondering and waiting their group assignment, we are concerned we may cause undue stress. Parents in the Intervention group will be introduced to a Parent Navigator while in the NICU, prior to discharge and following informed consent and enrollment. Parents can contact the Parent Navigator at any time after the initial meeting. If the Parent Navigator has not been contacted by the parent following enrollment or after discharge home from the NICU, the Parent Navigator will contact the parent within 2 business days after discharge to assess how the family is coping, answer questions, and provide necessary resources. For those randomized to the intervention group, the study staff will obtain a signed release to send an information sheet to the identified primary care physician to notify the provider that his/her patient has been enrolled in the study and will receive parent navigation services. The letter will clearly state the roles/responsibilities of the parent navigator.

The details of the intervention are as follows:

Navigator training: An established Parent Navigator program has been led by [name] (project coordinator), who is responsible for training and supervising Children's National Parent Navigator Program. Parent Navigators will be recruited specifically for serving families of NICU patients and will be the main source of the intervention in this study. Curriculum guide is attached in Documents Section.

Control Group: To assist with the transition to home care, families in the control group will be provided with the same care resource notebook.

End Points:

Our endpoints are:

1) Data collection: to enroll n=300 (n=150 in each group) and collect data for 12 months after NICU discharge.

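### The 99% power for a difference of 1 in median hospitalizations is unsupported: that effect does not determine the power of the planned rank-sum test, and no rate, distribution or loss allowance is stated

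*SAP*

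**What the plan says.** The Sample Size & Power paragraph has the same wording in both documents. It names hospitalizations over 12 months as the main infant outcome and says: "we estimate that we have excellent power (99%) to detect a difference of 1 in the median number of hospitalizations between the groups". The stated inputs are 300 families in two groups of 150 and an alpha of 0.05 with Bonferroni correction for three primary outcomes. The calculation counts 300 caregiver evaluations "and 300 NICU infant outcome evaluations". The paragraph concludes: "we believe that our sample size ensures sufficient power to measure clinically relevant differences between the intervention groups".

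For Aim 3, the SAP compares hospitalizations and ED visits between groups with the Wilcoxon–Mann–Whitney "two-sample rank-sum test, which is appropriate for use with nonparametric data, such as the count data from this aim". Birth weight, the stratification factor in the randomization, does not enter this test, although the Aim 1 model includes it.

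In the protocol's End Points, 300 is the enrolment target: "to enroll n=300 (n=150 in each group) and collect data for 12 months after NICU discharge". The SAP's Sensitivity Analyses paragraph foresees families lost to follow-up and allows an analysis "with the assumption that individuals with missing data have worse outcomes".

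**The concern.** Power for a rank-sum test depends on how the whole distribution of counts differs between the groups. The SAP gives only a difference in medians. When most infants have 0, 1 or 2 admissions, the median moves in whole steps. Medians of 1 and 0 say only that the share with any admission is above one half in one group and below it in the other, and both a trivial and a very large effect fit that description. The only source mentioned for the power figures is the published self-efficacy score distribution, which has no bearing on admissions.

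The SAP calls its assumptions conservative and names two. The correlation of 0.5 concerns the repeated scores in Aims 1 and 2. A 12-month admission total is one number per infant, so only the Bonferroni correction bears on this outcome. Counting every enrolled infant as evaluated is not conservative.

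The figure matters because the claim of sufficient power for the main infant outcome rests on it. If readers believe the trial had 99% power, they may take a null result as evidence that navigation does not reduce admissions. Under effects that fit the SAP's own description, power may have been moderate or low.

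**Working it through.** **Inputs from the documents.** 150 per group; alpha = 0.05/3 = 0.0167; rank-sum test on per-infant counts; medians differing by 1. Sidedness is not stated, and two-sided testing is assumed. All admission rates, distributions and losses below are assumptions.

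**Step 1: the stated figure.** The 99% cannot be recomputed, because no spread or distribution is given. One can solve for the SD it would need if every count shifted by 1. With z = 2.394 for alpha and 2.326 for 99% power:

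SD = 1 / [(2.394 + 2.326) × √(2/150)] = 1 / (4.720 × 0.1155) = 1.83

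For the rank-sum test on normal data (efficiency 3/π) this becomes 1.83 × √(3/π) = 1.79. Simulation with shifted Poisson counts agrees: 99% at SD 1.8, 97% at SD 2.0 and 84% at SD 2.5. Skewed counts tolerate more spread (negative binomial, SD 2.45: 99.8%). A reduction of exactly 1 in every count would also require that every control infant be admitted at least once.

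**Step 2: what the test responds to.** The rank-sum test measures θ = P(X>Y) + ½P(X=Y). Let shares a (control) and b (navigation) have any admission, with the same split of 1, 2 and 3 admissions among those admitted. Then

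θ = a(1−b) + ½[ab + (1−a)(1−b)] = ½ + (a−b)/2.

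The medians are 1 and 0 whenever a is above one half and b below it (and neither share is large enough to push a median to 2), so a−b can be anything from almost nothing upwards.

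**Step 3: power by hand.** Take a split of 0.60/0.25/0.15 and a pooled share admitted of 50%. The pooled proportions are 0.50, 0.30, 0.125 and 0.075, and the tie factor is 1 − (0.125 + 0.027 + 0.002 + 0.0004) = 0.846. The null standard error of θ is √[301/(12 × 150²) × 0.846] = 0.0307.

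- 55 vs 45%: 0.05/0.0307 = 1.63; Φ(1.63 − 2.394) = 22%.
- 60 vs 40%: 0.10/0.0307 = 3.26; Φ(0.86) = 81%.
- 65 vs 35%: 0.15/0.0307 = 4.89; Φ(2.49) = 99.4%.

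In this model, 99% power needs a−b = 2 × 4.720 × 0.0307 = 0.29, a gap of about 29 percentage points.

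**Step 4: simulation of the tie-corrected test, medians 1 and 0.** A loss of 20% leaves 150 × 0.8 = 120 per group.

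| Any admission, control vs navigation | 150 per group, alpha 0.0167 | 120 per group, alpha 0.0167 | 150 per group, alpha 0.05 |
|---|---|---|---|
| 51 vs 49% | 2% | 2% | 6% |
| 55 vs 45% | 22% | 17% | 37% |
| 60 vs 45% | 51% | 42% | 68% |
| 60 vs 40% | 82% | 71% | 91% |
| 65 vs 40% | 95% | 89% | 98% |
| 65 vs 35% | 99.5% | 98% | 99.9% |

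Repeat runs agree to within about 2 points. Other splits among admitted infants (0.80/0.15/0.05 or 0.40/0.30/0.30) move power by at most about 3 points.

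**Step 5: other distributions with medians differing by 1** (150 per group, alpha 0.0167). Poisson means 2 vs 1 or 3 vs 2: about 100%. Poisson 0.8 vs 0.6: 32%. Negative binomial (dispersion 1), means 3 vs 2: 57%; means 1.2 vs 0.8: 40%.

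**Step 6: whether the effect can occur.** If fewer than half of control infants are admitted, the control median is 0 and cannot fall by 1. The documents give no rate either way.

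**Step 7: the stratum.** Simulated at alpha 0.05 with a control mean of 0.8 per year, dispersion 1, 35% of infants in the low-weight stratum and a treatment rate ratio of 0.65. The rate ratio serves only to compare the two tests.

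| Admission rate ratio, low vs high weight | Unstratified | Stratified |
|---|---|---|
| 1 | 55% | 55% |
| 2 | 51% | 53% |
| 3 | 47% | 52% |
| 4 | 43% | 50% |

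With no treatment effect, the stratified test rejects 4.7 to 5.3% of the time at a nominal 5%.

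**The case against.** The strongest reply is that no arithmetic error has been shown. This is correct. The sample size, allocation, adjusted alpha, test and length of follow-up are all stated, so it would be too broad to say that the calculation has no inputs. What is missing is everything specific to hospitalizations, together with sidedness and loss.

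A second reply is that a difference of 1 can be read as a real shift in the counts, for which 99% is reasonable. Poisson means of 2 vs 1 or 3 vs 2 support this without requiring every infant to be admitted. However, the SAP does not say that this reading is meant, and overdispersed counts with the same median difference give much less.

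A reader might infer that the control median must be 0, since the protocol says "we will enroll all patients discharged from the CNMC NICU". The same section describes a Level IV unit with many complex cases, and the Specific Aims stress high care needs after discharge. Neither description amounts to an admission rate, so the question stays open.

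A reader might also infer from the SAP's silence that admission totals cut short by loss would be analysed as complete. The documents do not say so. That is a separate missing-data question and not part of this point.

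Finally, the birth-weight change can be called a preference: the unstratified test remains valid, and the gain depends on an assumed stratum effect. That stands. It is recommended because it follows the randomization and costs almost nothing.

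**Conclusion.** The 99% is unsupported, and the documents do not allow it to be checked. With medians of 1 and 0, 150 per group and two-sided alpha 0.0167, power runs from about 22% to 99.5% as the assumed gap in the share admitted widens from 10 to 30 points. A 20% loss would cost about 5, 11 and 1.5 points at 55 vs 45%, 60 vs 40% and 65 vs 35%. The result at 51 vs 49% is a boundary case that shows the ambiguity and is not a forecast. Using alpha 0.05 raises the figures but leaves the ambiguity.

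Two stronger readings should be resisted. The calculations do not show that 99% is false, because several plausible distributions reach it. Nor do they show that the trial is too small: the documents give no admission rate from which to judge that. What fails is the step from the stated effect to the claim of sufficient power.

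**What to change.** 1. Replace the 99% sentence in both documents with power simulated for the planned test. For example: with 150 infants per group ([n] after [d]% loss), two-sided alpha 0.0167 and the stratified rank-sum test, power is [y]% if [a]% of control and [b]% of navigation infants have at least one hospitalization, with [distribution] among those admitted. Give a short table over a plausible range of a and b, or of control rate and rate ratio, with and without expected loss. Limit the claim of sufficient power to those scenarios.

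2. Stratify the Aim 3 rank-sum tests for hospitalizations and ED visits by the birth-weight randomization stratum (van Elteren test). Under the assumptions above, this gains about 0 to 7 points of power at alpha 0.05. It also restores the nominal error rate when birth weight predicts admissions; ignoring a balanced prognostic stratum makes the unstratified test conservative.

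The cost is a short simulation, revised wording and a few lines of code. No new data are needed, since birth weight is already used to randomize. The downsides are that the stated power may be less favourable, and that stratification gains almost nothing if birth weight hardly predicts admissions.
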